5.2 Exclusion criteria

Subjects meeting any of the following criteria are not eligible for inclusion in this study.

1. Forms of psoriasis other than chronic plaque-type (e.g., pustular, erythrodermic, and guttate psoriasis) at Screening or Baseline
2. Drug-induced psoriasis (i.e., new onset or current exacerbation from beta-blockers, calcium channel inhibitors or lithium) at Screening or Baseline
3. Previous treatment with more than one TNF α inhibitor or with IL-17A (including secukinumab), IL-17R or IL-23 (including guselkumab) inhibitors

4. Use of other investigational drugs within 4 weeks before enrolment, or within a period of 5 half-lives of enrollment/initiation of the study treatment, whichever is longer
5. Ongoing use of prohibited treatments (see [Section 6.2.2](#))
6. Known immunosuppression (e.g., AIDS) at Screening or Baseline
7. History of an ongoing, chronic, or recurrent infectious disease, or evidence of tuberculosis (TB) infection as defined by a positive QuantiFERON TB-Gold test In-Tube assay (QFT) at Screening. Subjects with a positive or indeterminate QFT test may participate in the study if a full tuberculosis workup (according to local practice/guidelines) is completed within 12 weeks prior to randomization and conclusively establishes that the subject has no evidence of active tuberculosis. If presence of latent tuberculosis is established, then treatment must have been initiated and maintained according to local guidelines prior to randomization (see [Section 8.2.4](#))
8. History of hepatitis B, hepatitis C, or HIV infection
9. History of congestive heart failure (NYHA functional classification \geq III) at Screening or Baseline
10. Uncontrolled hypertension (systolic \geq 160 mmHg, diastolic \geq 95 mmHg)
11. History of hypersensitivity to any of the study treatments or its excipients or to any human or humanized biological agents (antibody or soluble receptor) at Screening including reactions to local anesthetics required to perform skin biopsy
12. History or evidence of ongoing alcohol or drug abuse, within the last 6 months before Baseline
13. Any live vaccines (including nasal-spray flu vaccine) starting from 6 weeks prior to initial treatment administration and during the study period
14. Pregnant or nursing (lactating) women, where pregnancy is defined as the state of a female after conception and until the termination of gestation, confirmed by a positive human chorionic gonadotropin (hCG) laboratory test (> 5 mIU/mL)

Women of childbearing potential, defined as all women physiologically capable of becoming pregnant, unless they are using effective methods of contraception during the study or longer if required by locally-approved prescribing information (e.g., 20 weeks in the European Union and countries where applicable for secukinumab). Effective contraception methods include:

- total abstinence (when this is in line with the preferred and usual lifestyle of the subject). Periodic abstinence (e.g., calendar, ovulation, symptothermal, post-ovulation methods) and withdrawal are not acceptable methods of contraception
- female sterilization (have had surgical bilateral oophorectomy with or without hysterectomy) total hysterectomy or tubal ligation at least 6 weeks before taking study treatment. In case of oophorectomy alone, only when the reproductive status of the woman has been confirmed by follow up hormone level assessment
- male sterilization (at least 6 months prior to Screening). For female subjects on the study, the vasectomized male partner should be the sole partner for that subject
- barrier methods of contraception: condom or occlusive cap (diaphragm or cervical/vault caps). For countries where applicable, the use of spermicidal foam/gel/film/cream/vaginal suppository will be allowed

- use of oral (estrogen and progesterone), injected, or implanted hormonal methods of contraception or placement of an intrauterine device or intrauterine system or other forms of hormonal contraception that have comparable efficacy (failure rate < 1%), for example hormone vaginal ring or transdermal hormone contraception

In case of use of oral contraception, women should have been stable on the same pill for a minimum of 12 weeks before taking study treatment.

Women are considered post-menopausal and not of childbearing potential if they have had 12 months of natural (spontaneous) amenorrhea with an appropriate clinical profile (e.g., age appropriate history of vasomotor symptoms) or have had surgical bilateral oophorectomy (with or without hysterectomy), total hysterectomy or tubal ligation at least 6 weeks ago. In the case of oophorectomy alone, only when the reproductive status of the woman has been confirmed by follow-up hormone level assessment is she considered not of childbearing potential.

If local regulations deviate from the contraception methods listed above to prevent pregnancy, local regulations apply and will be described in the informed consent form.

15. History of lymphoproliferative disease or any known malignancy or history of malignancy of any organ system treated or untreated within the past 5 years, regardless of whether there is evidence of local recurrence or metastases (except for skin Bowen's disease, or basal cell carcinoma or actinic keratosis that have been treated with no evidence of recurrence in the past 12 weeks; carcinoma *in situ* of the cervix or non-invasive malignant colon polyps that have been removed)
16. Underlying conditions (including, but not limited to metabolic, hematologic, renal, hepatic, pulmonary, neurologic, endocrine, cardiac, infectious or gastrointestinal) which in the opinion of the Investigator significantly immunocompromise the subject and/or places the subject at unacceptable risk for receiving an immunomodulatory therapy. In addition, current severe progressive or uncontrolled diseases which render the subject unsuitable for the study or put the subject at increased risk, including any medical or psychiatric condition which, in the Investigator's opinion, would preclude the participant from adhering to the protocol or completing the study per protocol
17. Inability or unwillingness to undergo study procedures, including venipunctures and skin biopsy

No additional exclusions may be applied by the Investigator in order to ensure that the study population will be representative of all eligible subjects.

6 Treatment

6.1 Study treatment

6.1.1 Investigational and control drugs

Table 6-1 Investigational and control drug

Investigational/ control drug (name and strength)	Pharmaceutical dosage form	Route of administration	Supply type	Sponsor (global or local)
Secukinumab 300 mg	Solution for injection in pre-filled syringe	s.c use	Open label subject packs; pre-filled syringes	Sponsor global
Guselkumab 100 mg	Solution for injection in pre-filled syringe	s.c use	Open label subject packs; pre-filled syringes	Sponsor global

6.1.2 Additional study treatments

No other treatment beyond investigational drug and control drug are included in this study.

6.1.3 Treatment arms

At Baseline, subjects will be randomized to one of the 2 treatment arms in a 1:1 ratio ([Figure 3-1](#)).

Secukinumab treatment arm: 20 subjects with plaque psoriasis with an inadequate response to ustekinumab will self-administer 300 mg secukinumab as two 150-mg s.c. injections at Baseline, Weeks 1, 2, 3, 4 and then every 4 weeks until Week 12 inclusive.

Guselkumab treatment arm: 20 subjects with plaque psoriasis with an inadequate response to ustekinumab will self-administer guselkumab as 100-mg s.c. injections at Baseline, Weeks 4, and 12.

[figure not shown]
The initiation of secukinumab and guselkumab should not happen earlier than 12 weeks from the last administration of ustekinumab.

6.1.4 Treatment duration

The planned duration of treatment is 16 weeks.

6.2 Other treatments

No additional treatment is included in this study.

6.2.1 Concomitant therapy

All medications, procedures and significant non-drug therapies (including physical therapy and blood transfusions) administered after the subject is enrolled in the study must be recorded on the appropriate eCRF.

Each concomitant drug must be individually assessed against all exclusion criteria/prohibited medication. If in doubt, the Investigator should contact the Novartis medical monitor before randomizing a subject or allowing a new medication to be started. If the subject is already enrolled, contact Novartis to determine if the subject should continue participation in the study.

6.2.2 Prohibited medication

Use of topical pharmaceutically active treatment will not be allowed for the entire duration of the study, with the exception of mild topical treatments applied to the face, scalp, and/or genitoanal area.

Use of the treatments displayed in [Table 6-2](#) prior to study start (period specified in the table) or after study start will not be allowed.

Table 6-2 Prohibited medication

Prohibited treatments	Prohibition period before Baseline ^a
Any biologic drug directly targeting IL-17 or any IL-17 receptor or IL-23 (e.g., secukinumab, brodalumab, ixekizumab, guselkumab, risankizumab)	No prior use allowed
TNF α inhibitors (if more than one have been used)	Prior use of one inhibitor allowed. None allowed after Baseline
Any biological immunomodulatory agent other than the above listed (e.g., alefacept, briakinumab, efalizumab)	6 months
Other systemic immunomodulatory treatments ^b (e.g., methotrexate, cyclosporine A, glucocorticosteroids, cyclophosphamide) and any treatment for psoriatic arthritis, except for NSAIDs	4 weeks
Other systemic psoriasis treatments (e.g., retinoids, fumarates, apremilast)	4 weeks
Photo-chemotherapy (e.g., psoralen plus UVA)	4 weeks
Phototherapy (e.g., UVA, UVB)	2 weeks
Live virus vaccinations	6 weeks
Any investigational treatment or participation in any interventional study	4 weeks or 5 half-lives (whichever is longer)

a) In case of undue safety risk for the subjects, they should discontinue study treatment at the discretion of the Investigator or qualified site staff. If subjects treated with secukinumab receive a live virus vaccination during the study, they must discontinue study treatment

b) Inhalational steroids with only a topical effect (e.g., to treat asthma) are not considered systemic immunomodulatory treatments and are therefore acceptable

NSAID = nonsteroidal anti-inflammatory drug, UVA = ultraviolet light A, UVB = ultraviolet light B

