Inadequate responders are defined as subjects who, after treatment with ustekinumab at a dose equal or higher than that on the label for at least 24 weeks, present a PASI of 1-10 and one or more refractory skin plaques, defined by a TCS of at least 6 and an area ≥ 10 cm² at Baseline.

[figure not shown]
At Baseline (Day 1), subjects will be randomized to treatment with secukinumab or guselkumab in a 1:1 ratio. Secukinumab will be self-administered as two 150-mg s.c. injections at Baseline, Weeks 1, 2, 3, 4 and then every 4 weeks until Week 12 inclusive. Guselkumab will be self-administered as 100-mg s.c. injections at Baseline, Weeks 4, and 12. The initiation of study treatment at Baseline should not happen earlier than 12 weeks after the last administration of ustekinumab.

Forty subjects will be enrolled and treated for 16 weeks. Additional unscheduled visits can be called by the Investigators according to their own judgement and personal clinical experience.

At Baseline, two 6-mm punch biopsies will be taken from all the subjects, one from the identified active plaque (TCS ≥ 6) and one from never-lesional skin. At the End-of-study Visit, one biopsy will be taken from the same area of the active plaque sampled at Baseline. Whenever possible, biopsies should be taken from the trunk to avoid scars in exposed body areas.

The duration of enrollment is expected to be 6 months. The design of the study is outlined in [Figure 3-1](#).

Figure 3-1 Study design

4 Rationale

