5.1 Inclusion criteria

Subjects eligible for inclusion in this study must meet **all** of the following criteria:

1. Signed informed consent must be obtained prior to participation in the study
2. Men or women \geq 18 years of age at the time of consent
3. Chronic plaque-type psoriasis considered inadequately controlled after treatment with ustekinumab according to the following criteria:
 - ustekinumab administered at a dose equal or higher than that on the label for at least 24 weeks. The last administration must be at least 12 weeks before randomization
 - absolute PASI score of 1-10 at Screening
4. Presence of at least 1 refractory skin plaque, defined by a TCS of at least 6 and severity score of at least 2 or 3 (moderate) for each individual item, with an area \geq 10 cm² at Screening and Baseline

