8.3 Efficacy

8.3.1 Total clinical score

The TCS will be assessed at all study visits as indicated in Table 8-1. At Baseline, it should be performed before the first administration of study treatment.

The TCS for each plaque will be determined (ideally by the same evaluator) as the sum of 3 scores: erythema (0-3), scaling (0-3) and infiltration (0-3) rated according to their severity as shown in Table 8-2. The TCS can range from 0 (all signs absent) to 9 (all signs severe).

Table 8-2 Assessments of total clinical score

Score	Intensity	Erythema	Scaling	Infiltration
0	No evidence	Normal skin color	No scaling	No infiltration
0.5	Doubtful or very mild			
1.0	Mild	Pink/light red	Slight roughness, mainly fine scales	Slight definite infiltration
1.5	Mild to moderate			
2.0	Moderate	Red	Coarse scaling	Moderate infiltration
2.5	Moderate to severe			
3.0	Severe	Intense red	Coarse, thick scales	Very marked infiltration

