12.4 Analysis of the primary endpoint

12.4.1 Definition of primary endpoint

The primary objective is to assess the superiority of secukinumab over guselkumab in controlling clinical activity in psoriatic plaques resistant to treatment with ustekinumab.

The primary endpoint is the proportion of subjects whose plaque achieves “clear” or “almost clear” status (TCS = 0-2) by 16 weeks of treatment with secukinumab or guselkumab.

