12.4.2 Statistical model, hypothesis, and method of analysis

The number (%) of subjects whose plaques achieve “clear” or “almost clear” status (TCS = 0-2) at Week 16 (i.e., responders) will be provided based on the FAS together with the 95% confidence interval using the exact method for the difference in proportions of responders in each arm.

Furthermore, a 1-sided Fisher’s exact test for the difference in the proportions of responders in the secukinumab (P1) and gesulkumab (P2) arms, $H_0: P_1 - P_2 = 0$ versus $H_1: P_1 - P_2 > 0$ at a Type I error rate of 0.05 will be performed.

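### The target plaque may lie on the face, scalp or genitoanal area, where mild topical treatment stays allowed, so topical use could contribute to a counted response

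*Protocol*

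**What the plan says.** **Which plaque qualifies.** Protocol Section 5.1, criterion 4, asks for "Presence of at least 1 refractory skin plaque, defined by a TCS of at least 6". It adds a minimum severity for each item and an area of at least 10 cm². No body site is named or excluded.

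**Which plaque is scored.** Section 12.4.1 states: "The primary endpoint is the proportion of subjects whose plaque achieves" a TCS of 0-2. Table 8-1 schedules the TCS of a single target plaque from Screening onwards. Section 8.3.1 is broader ("The TCS for each plaque will be determined"), and Section 12.4.2 uses the plural ("subjects whose plaques achieve").

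**Where the plaque should be.** The only text on location is in Section 3 (Study design), repeated in a footnote to Table 8-1: "Whenever possible, biopsies should be taken from the trunk to avoid scars in exposed body areas". At the End-of-study Visit, "one biopsy will be taken from the same area of the active plaque sampled at Baseline".

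**Which topicals are allowed.** Section 6.2.2 bans active topical treatment for the whole study, "with the exception of mild topical treatments applied to the face, scalp, and/or genitoanal area". It makes no separate provision for the target plaque.

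**Who knows the treatment.** Under Section 6.4, subjects, site staff and the trial team know the allocation. Efficacy assessors are blinded.

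**The concern.** An exemption for a few body areas does limited harm when the outcome is a whole-body score. Here one plaque decides whether a subject is a responder. If that plaque lies in an exempt area, a permitted topical acts directly on the outcome, and any improvement is credited to secukinumab or guselkumab.

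The open-label design makes this more than added noise. A subject or site that knows the allocation may use a topical more readily in one arm than in the other. A blinded assessor scores what is on the skin, so blinding protects against biased scoring but not against unequal co-treatment of the scored lesion. With 20 subjects per arm, each responder is 1/20 = 5 percentage points, so one or two such cases matter.

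**Working it through.** **Step 1: does any rule in the protocol close the gap?**
- Criterion 4 defines the plaque by TCS, item severity and area. It does not address site.
- The trunk wording in Section 3 and Table 8-1 applies where possible and is there to avoid scars. The lesional biopsy comes from the identified active plaque, so the wording steers the choice of plaque, but it bars none of the exempt areas.
- Section 9.1.1 stops study treatment for use of a prohibited treatment. A mild topical in an exempt area is not prohibited, so it triggers nothing.
- Section 12.4.3 deals with discontinuation only. Section 12.4.4 removes the imputation but does not address topical use.
- Section 6.2.1 has all medication recorded. This documents the use but does not change responder status.

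No visible text keeps a topically treated target plaque from counting as a response.

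**Step 2: reproduce the plan's power.** Inputs from Section 12.9.1 are n = 20 per arm, a 1-sided Fisher's exact test at 0.05, P1 = 0.75 (secukinumab) and P2 = 0.35 (guselkumab). With x and y the numbers of responders,

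Power = Σ Bin(x; 20, P1) × Bin(y; 20, P2), summed over all (x, y) whose 1-sided hypergeometric p-value is ≤ 0.05.

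This gives 72.4%, against 72% in Table 12-1. The other six rows of the table also reproduce.

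**Step 3: the effect of one or two extra responders in one arm.** The true rate in that arm is moved by 5 or 10 points (1/20 or 2/20), which is one or two extra responders on average. How many would occur is an assumption.

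| True rates, secukinumab / guselkumab | Meaning | Rejection probability |
|---|---|---|
| 0.50 / 0.50 | no difference | 2.1% |
| 0.55 / 0.50 | one extra on secukinumab | 4.4% |
| 0.60 / 0.50 | two extra on secukinumab | 8.3% |
| 0.35 / 0.35 | no difference, at the plan's guselkumab rate | 2.6% |
| 0.45 / 0.35 | two extra on secukinumab | 9.0% |
| 0.75 / 0.35 | the plan's scenario | 72.4% |
| 0.75 / 0.40 | one extra on guselkumab | 61.0% |
| 0.75 / 0.45 | two extra on guselkumab | 49.1% |

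**Step 4: equal topical use in both arms.** Let f be the share of target plaques that lie in an exempt area and are treated topically, and r the share of their non-responders that become responders. Both are assumed. Then P1' = 0.75 + f·r·0.25 and P2' = 0.35 + f·r·0.65. The guselkumab arm gains more because it has more non-responders.
- f = 0.10, r = 0.5: 0.7625 v 0.3825, difference 38 points, power 68.6%.
- f = 0.20, r = 0.5: 0.775 v 0.415, difference 36 points, power 65.0%.
- f = 0.30, r = 1: 0.825 v 0.545, difference 28 points, power 50.1%. This is an extreme case.

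Even balanced use therefore shrinks the difference that the trial is designed to detect.

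**The case against.** **The target plaque is largely fixed already.** Sections 3 and 8.3.3 and Table 8-1 describe one identified active plaque, biopsied at Baseline and again in the same area at the end, and scored as the target from Screening. Section 12.4.1 uses the singular. A reader might infer from the plural in Section 12.4.2 that the endpoint plaque is undefined, but the documents do not support that, and the plural can be read as grammar. What remains open is the body site of that plaque, and which plaque to choose when several qualify.

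**The trunk preference makes the case uncommon.** Siting the biopsy sites the plaque, so an exempt-area target is a residual case, possibly with a frequency of zero. This stands as a limit on size. It does not close the gap, because a preference permits exceptions.

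**Only mild topicals are exempt.** A target starts at a TCS of at least 6 and must reach 0-2. A reader might infer that a topical alone could meet the endpoint. Nothing in the documents shows that a mild topical can do this. The supportable statement is that it could contribute to a counted response.

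**The direction is unknown.** A reader might infer that the gap favours secukinumab. The inflated rejection rates in the table hold only if the extra responders fall in that arm. In the guselkumab arm, or in both arms equally, the harm is lost power.

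**It may be handled elsewhere.** Some text around Section 8.3 is redacted, and a site rule there cannot be excluded. The statistical analysis plan was not available and could say how topical use affects responder status. It could not change which plaque the site chose at Screening.

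**Conclusion.** The point holds as a narrow gap. Followed as written, the protocol allows a target plaque in an area where mild topical treatment is permitted, and it counts that plaque's improvement towards the primary endpoint. With open-label treatment the use may differ by arm, and blinded assessment does not remove it.

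The size is conditional. It rests on an assumed number of affected subjects, on the topical having enough effect to change a responder status, and on the arm in which this happens. Two extra secukinumab responders on average lift the rejection rate under equal true rates from about 2-3% to 8-9%, above the nominal 5%. One extra at 50% stays below it, at 4.4%. Two extra guselkumab responders take power from 72% to 49%.

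The documents do not show that such cases will be common, or that the result would lean one way. Because 20 per arm leaves so little room and the remedy is cheap, the gap should be closed before enrolment.

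**What to change.** Reconcile Section 3, criterion 4 in Section 5.1, Section 6.2.2 and Table 8-1 on the location of the target plaque:
- State that each subject has one target plaque, recorded before randomisation, which is also the plaque biopsied.
- Require that this plaque lies outside the face, scalp and genitoanal area.
- Where several plaques qualify, keep the existing trunk preference. Choosing by highest TCS instead could select an exposed limb over the trunk and so conflict with the scar-avoidance wording.
- Refer to that one plaque in Sections 12.4.1 and 12.4.2, and align the wording of Section 8.3.1.

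The rules on topical use stay as they are.

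The cost is amended wording, an eCRF field for plaque location and a small narrowing of eligibility, because a subject whose only qualifying plaque is in an exempt area could not be included. The trunk preference suggests that few subjects would be lost, but the protocol gives no figure. Sample size and test are unchanged.

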6.3 Subject numbering, treatment assignment, randomization

6.3.1 Subject numbering

Each subject will be identified in the study by a subject number, which is assigned when the subject is first enrolled for screening and is retained as the primary identifier for the subjects throughout their entire participation in the study. The subject number consists of the study site number (assigned by Novartis to the study site) with a sequential subject number suffixed to it, so that each subject is numbered uniquely across the entire database. Upon signing the informed consent form, the subject is assigned to the next sequential subject number available.

